Presurgical MRI will be done on a 3T MRI (Prisma Siemens MRI scanner) or 1.5T (Achiva, Phillips MRI scanner). The protocol for patients less than 18 months of age will be Sagittal T1, Axial inversion recovery (IR), T2, fluid-attenuated inversion recovery (FLAIR), susceptibility weighted image (SWI), diffusion weighted images (DWI), diffusion tensor imaging (DTI), resting state fMRI, and sagittal 3D GRE / FFE (on 1.5 T scanners) or 3D T1 VIBE (on 3T scanner).

The MRI protocol for patients over 18 months of age will be: Sagittal T1, coronal T2, Axial T2, fluid-attenuated inversion recovery (FLAIR), susceptibility weighted image (SWI), diffusion weighted images (DWI), diffusion tensor imaging (DTI), resting state fMRI, and sagittal 3D GRE / FFE (on 1.5 T scanners) or 3D T1 VIBE (on 3T scanner).

Post-processing of the acquired 3D GRE, FFE and T1VIBE sequences will be done on vitrea station. The acquired images will be reviewed by US board-certified pediatric neuroradiologists for single or multi suture craniosynostosis. Intracranial volume, ventricular size and sulcal crowding will be accessed. The DTI data will be analyzed on a password protected workstation by MRI physicist (Co-investigator, [name] and his research assistant, [name]) for evaluation of white matter microstructural integrity. Other imaging data from the same MRI sequences may also be exported to the workstation for additional quantitative analysis.

The expected time for MRI image acquisition is approximately 60 minutes for control subjects. If this process is prolonged greater than 2 hours due to control subject's lack of cooperation or discomfort then it will be aborted and will be re-scheduled. If the parents do not wish to proceed with a rescheduled time then the control subject will be removed from the study.

The MRI protocols will be identical for the control subjects and scheduled at the parent's convenience, but falling within one week on either side of their requested age. Because scheduling of the MRI may not allow this degree of control, control patients will be stratified by the age when they actually undergo the study not the age of recruitment. We will not plan to sedate the normal control subjects, however, sedation *may be a*

Title: Neurodevelopmental Outcomes in Craniosynostosis Repair
PI: [name]
Site: Arkansas Children's Hospital
Funding: UAMS Intramural Grant

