- pre-anesthesia testing (45-minute duration) & pre-operative phlebotomy including, type and screen (2-4ml), complete blood count (CBC) (0.5ml), and possibly basic metabolic panel (0.5ml), and coagulation panel (2-4ml)
- initial neurodevelopmental testing (Bayley and Mullen Scales – 1 hour duration performed by [name]. [name])
- preoperative MRI functional sequences (60 minute duration) (research-related)

2. Surgery Day: Two cohorts:

- endoscopic-assisted group (age range at surgery between 3- and 6-months old) and
- Open cranial vault remodeling group (age range at surgery between 6- and 24-months old).

3. Six (6) to 6-months post-op:

- clinic visit,
- Neurodevelopmental testing (research-related)
- repeat MRI Imaging(60 minute duration) (research-related)

4. Twelve (12-) to 18-months post-op:

- clinic visit,
- Neurodevelopmental testing (may be repeated earlier at 9-15 months if clinically indicated) (research-related)
- Repeat MRI imaging(60 minute duration) (research-related)

5. Pre-school age (4 years old and younger):

- clinic visit
- Neurodevelopmental testing (research-related)
- repeat MRI Imaging(60 minute duration) (research-related)

Risks and Benefits

One potential risk to study participants is the potential for loss of confidentiality. Measures to protect the confidentiality of study participants will be implemented as described in the Data Handling and Recordkeeping section below. Another potential small risk is the additional anesthesia for the research related MRI's both in terms of the subjective experience of the test subjects themselves and risk of administering

Title: Neurodevelopmental Outcomes in Craniosynostosis Repair
PI: [name]
Site: Arkansas Children's Hospital
Funding: UAMS Intramural Grant

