All these studies must be considered with the following factors. For one thing, it is impossible to separate some of the confounding factors to isolate the causative effect of anesthesia from others, most notably the surgery itself. Two, some other factors such as sex and maternal education have been shown to have a much stronger influence on all measurable neurodevelopmental outcomes than the measurable associations of anesthetic. Many of the other health and social factors that would necessitate multiple surgeries (and anesthetics) for whatever reason, may contribute to a larger extent to these measurable outcomes. Thus, there is mixed evidence at best, that there is a significant risk to neurodevelopmental outcomes of the exposure to general anesthetic in this patient population, particular in this study with a maximum of three additional exposures totaling approximately 90 minutes. This is all the more important to consider in the context that it will be impossible to state whether the child's potential developmental problems, were from the craniosynostosis, the anesthesia or any subsequent anesthetic exposures. It is important to note that the duration of anesthesia in the test subjects undergoing surgery will be anywhere from 2 hours to 5 hours and thus 4-10 times longer than any MRI with sedation they might have after. Moreover, if those patients need sedation they will receive it an older age (i.e. post-op) where there is arguably less change of any further anesthetic exposure affecting development.

Title: Neurodevelopmental Outcomes in Craniosynostosis Repair
PI: [name]
Site: Arkansas Children's Hospital
Funding: UAMS Intramural Grant

As stated, our team will attempt non-pharmacologic calming methods with ALL patients first but will clearly explain to parents the small additional risk of additional MRI's if sedation is necessary. There is a benefit of avoiding the routine use of radiation to diagnose the craniosynostosis, as we would elect to obtain the 'black-bone MRI' pre-operatively which has windowing that emulates the look of a CT scan, enabling easier interpretation.

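### The risk section's sedation exposure for research MRIs (about 90 minutes over three scans) implies 30 minutes per scan, but the schedule lists 60

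*Combined protocol and SAP*

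**What the plan says.** Risks and Benefits makes two statements about how long a patient may be anesthetized for post-operative study MRIs. When concluding that the evidence of harm is mixed, it adds "particular in this study with a maximum of three additional exposures totaling approximately 90 minutes". It then says that anesthesia for the surgery itself "will be anywhere from 2 hours to 5 hours and thus 4-10 times longer than any MRI with sedation they might have after".

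The Schedule of Imaging and Neurodevelopmental Assessment lists three post-operative MRIs, in items 3, 4 and 5. Items 3 and 5 read "repeat MRI Imaging(60 minute duration) (research-related", and item 4 gives the same 60 minutes.

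The Radiological Component bears on this in two ways. It says "The expected time for MRI image acquisition is approximately 60 minutes for control subjects" and describes the MRI protocols as identical for controls. It also says the three post-operative MRIs are done for research.

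Sedation is a fallback: Risks and Benefits says calming techniques without drugs are tried first in every child.

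**The concern.** The two statements in the risk section agree with each other but not with the schedule. Both rest on 30 minutes per scan, half the listed duration. Two separate figures give the same 30 minutes, so a single mistyped digit does not explain the gap, and a factor of two is more than an approximation can cover.

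The figure matters because the post-operative scans are research procedures, so any sedation for them is a research risk. The same section quotes the regulator's warning about repeated or lengthy anesthesia in children under 3, and then uses the short total as a study-specific reason for reassurance. It also says the small added risk will be explained to parents. If the scheduled duration is right, the reassurance uses half the scan time that a child sedated at every visit would have.

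**Working it through.** **Inputs**

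- Risks and Benefits: at most 3 additional exposures, about 90 minutes in total; surgical anesthesia of 2 to 5 hours (120 to 300 minutes); stated ratio of surgery to one sedated MRI of 4 to 10.
- Schedule, items 3, 4 and 5: 60 minutes for each post-operative MRI.
- The pre-operative MRI is outside the three additional exposures and is not counted.

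**Reproducing the stated figures**

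- Time per scan = total / number = 90/3 = 30 minutes.
- Ratio = surgery / one scan: 120/30 = 4 and 300/30 = 10. This matches the stated range exactly.
- Against the 90-minute total the ratio would be 120/90 = 1.3 to 300/90 = 3.3, so the stated 4 to 10 is a per-scan ratio.

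**At the scheduled duration**

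- Total scan time = 3 × 60 = 180 minutes; 180/90 = 2.0 times the stated total.
- Ratio: 120/60 = 2 and 300/60 = 5.

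**Sensitivity to the time under sedation per scan** (45 and 75 minutes are assumptions)

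| Minutes per scan | Three-scan total | Surgery / one scan |
|---|---|---|
| 30 (implied by risk section) | 90 | 4 to 10 |
| 45 | 135 | 2.7 to 6.7 |
| 60 (schedule) | 180 | 2 to 5 |
| 75 | 225 | 1.6 to 4 |

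**Three-scan total against surgery**

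- At 90 minutes: 90/300 = 30% to 90/120 = 75% of surgical anesthesia.
- At 180 minutes: 180/300 = 60% to 180/120 = 150%.
- The total exceeds a 2-hour operation once a scan takes more than 120/3 = 40 minutes. At 60 minutes per scan it exceeds any operation shorter than 3 hours.

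**One scan against the exposures the protocol cites**

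The randomized trial cited as reassuring had a median of 54 minutes, and another cited study had a mean of 80 minutes. The order is 30 < 54 < 60 < 80: a 30-minute scan is below the trial's median and a 60-minute scan is above it. For multiple exposures, the cited birth cohort had a median of 75 and a mean of 133 minutes, and a single 60-minute scan is below both.

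**Ages at the scans**

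This does not decide between 30 and 60 minutes. It shows whether the under-3 warning applies.

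- Surgery ages: "endoscopic-assisted group (age range at surgery between 3- and 6-months old" for one cohort, and "age range at surgery between 6- and 24-months old" for the open cohort.
- First scan: the window reads "Six (6) to 6-months post-op", so its upper end is unclear. If it means 6 months, ages are 9–12 months (endoscopic) and 12–30 months (open). If it is assumed to run to 12 months, where the next window starts, they are 9–18 and 12–36 months.
- Second scan: "Twelve (12-) to 18-months post-op" gives 15–24 months (endoscopic) and 18–42 months (open).

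In the endoscopic group the first two scans therefore fall under age 3 on either reading. In the open group, the first scan is under 3 for every child only on the 6-month reading. The third scan has no fixed age below 4 years and is not counted.

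**The case against.** The strongest reply is that the two places measure different things: the risk section gives anesthetic exposure and the schedule gives MRI duration. The schedule also attaches durations to other visit components, such as pre-anesthesia testing, so 60 minutes could be an appointment slot with a shorter time under sedation. This cannot be ruled out. Two points count against it. The Radiological Component gives about 60 minutes for image acquisition itself under identical protocols, although that sentence concerns unsedated controls and is only supporting evidence. And nowhere does the protocol describe a shortened sequence set, a 30-minute scan, or sedation for part of a scan. It follows that 180 minutes is scan time. Anesthetic time could be longer, if induction and emergence are added, or shorter, if 60 minutes is a slot.

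A second reply is that the consequences are modest, and much of this stands. The protocol's own comparison keeps its direction, since surgery is still longer than one scan. Setting the three-scan total against surgery, or one scan against the 54-minute median, are comparisons made here and not in the protocol. The second crosses by only 6 minutes, and the other cited durations remain above 60. The section's conclusion rests mainly on the human studies and on confounding. Nor does anything in the available text show that parents are given the 90-minute figure: the sedation risks listed for explanation to them include no duration.

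These replies limit the consequence. They do not reconcile the two durations.

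**Conclusion.** The concern holds. The stated 90 minutes and 4 to 10 times both require 30-minute scans, while the schedule gives 60 minutes for all three post-operative MRIs. On the schedule, the maximum is 180 minutes of scan time (2.0 times the stated total) and surgery is 2 to 5 times one scan.

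This assumes a child sedated at all three scans, for the full listed duration of each. The documents do not show which duration is intended, only that the two are unreconciled. They also give no risk per minute or per exposure for this study, so any added harm cannot be calculated.

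The risk argument is weakened and not reversed. Because this is a stated safety figure for research sedation of infants and may be understated twofold, it should be fixed.

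**What to change.** Decide which duration is correct and make the two sections agree.

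- **If 60 minutes stands:** restate the figure in Risks and Benefits as up to three additional exposures totaling about 180 minutes of scan time for a child sedated at every post-operative MRI, with surgery 2 to 5 times as long as one scan.
- **If a sedated scan of about 30 minutes is intended:** say so, justify it (for example, by naming the shortened sequence set), and correct the schedule for sedated scans.
- **In either case:** give expected anesthetic time separately from scan time, stating whether induction and emergence are included, and align any duration that appears in the consent text.

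This is a wording amendment to the risk section or the schedule. If 60 minutes stands, procedures, visits and analysis are unchanged, and the only cost is a less favourable stated exposure.

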A master key list of study subject identifiers including names, MRNs, and five-digit study IDNs will be maintained on a password protected computer. As this is a study at ACH, we will also be registering test and control subjects into the Clinical Trials Management System. The study subject identifiers will not be linked to the study data. All study subject identifiers in the master list will be destroyed after publication. De-identified study data will be backed up by maintaining a copy on the computer of the principal investigator [name] and co-investigator [name] MBBS, with the original on the ACH password-protected shared drive server. De-identifiable study data will be retained indefinitely.

Regarding the data from other sites, only de-identified, data will be pooled for analysis, ie quantitative data from the DTI analysis and neurodevelopmental results. Each outside site, will be responsible for de-identifying its own data set for pooling with ours. UAMS will be the repository for the data analysis, and the central database we will keep will ONLY contain the 5-digit IDN. Each institution will retain its key for the IDN and corresponding patient identifiers.

The data safety monitor(DSM) will be an appointed clinical team member, ([name], PA) who will NOT be responsible for recruiting patients into the study but rather have the role of communicating with the PI's mentioned above ([name] [name]) and study coordinator about unanticipated problems, deviations from protocols and/or modifications. If an AE or SAE occurs as defined in the section above to any subject in the study, the study coordinator will relay this information to the IRB in the appropriate time frame but also will notify the DSM to make note in routine reports to the IRB on study progress.

Data Analysis

Primary and Secondary Endpoints

- 1) Understand to a previously unreported level of detail the brain function in children with craniosynostosis using DTI-MRI sequences as compared with age-matched controls
- 2) Determine the effect of CVR on brain development in comparing pre and post-operation DTI-MRI sequences at several intervals post-operatively
- 3) Identify the relationship between the brain development changes as seen on DTI with cognitive testing results

Note that from this master group, multiple cohorts will be grouped for analysis, i.e., single suture and multiple suture craniosynostosis, syndromic craniosynostosis. We

Title: Neurodevelopmental Outcomes in Craniosynostosis Repair
PI: [name]
Site: Arkansas Children's Hospital
Funding: UAMS Intramural Grant

plan to analyze data both for quality control and preliminary analysis every 6 months while the study is on-going.

Statistical Methods

For the complex analysis of large amounts of MRI data on the same patient and comparing with other patients, we plan to employ biostatistical support baseline and demographic characteristics will be summarized by standard descriptive summaries (e.g., means and standard deviations for continuous variables such as age and percentages for categorical variables such as gender).

Data will be presented as frequencies, medians with ranges, or \pm SD, as appropriate. Tests of group differences will include the paired t-test, χ^2 , and z-test, as appropriate. Repeated measures analysis will also be performed to on pre- and post-operative data for the same patient.

DTI parameters will be computed by standard software and will be compared between patients and controls or between different ages using standard statistical methods. Of note, for each MRI session, whether or not the participant was sedated will be a variable including in analysis.

Ethical Considerations

This study will be conducted in accordance with all applicable government regulations and Arkansas Children's Hospital research policies and procedures. This protocol and any amendments will be submitted and approved by the UAMS Institutional Review Board (IRB) to conduct the study.

The formal consent of each caregiver for their child, using the IRB-approved consent form, will be obtained before that subject is submitted to any study procedure. The caregivers of all subjects for this study will be provided a consent form describing this study and providing sufficient information in language suitable for subjects to make an informed decision about their participation in this study. The person obtaining consent will thoroughly explain each element of the document and outline the risks and benefits, alternate treatment(s), and requirements of the study.

The consent process will take place in a quiet and private room, and caregivers may take as much time as needed to make a decision about their participation. Participation privacy will be maintained and questions regarding participation will be answered. No coercion or undue influence will be used in the consent process. This consent form must be signed by the subject or legally authorized representative and the individual obtaining the consent. A copy of the signed consent will be given to the participant, and the informed consent process will be documented in each subject's research record. If

Title: Neurodevelopmental Outcomes in Craniosynostosis Repair
PI: [name]
Site: Arkansas Children's Hospital
Funding: UAMS Intramural Grant

assent is required, include a statement that assent will be obtained and that assenting minors will be consented if they reach the age of majority during the study.

Dissemination of Data

Results of this study may be used for presentations, posters, or publications. The publications will not contain any identifiable information that could be linked to a participant. Once all de-identified information has been stripped, the data from this study may be pooled for statistical analysis with the data from our collaborators, Wake Forest, Yale University Departments of Plastic Surgery, and Vanderbilt Department of Plastic Surgery.

Compensation of study participants (including new and existing subjects and controls):

1. Given the changing economical resources of our participants due to pandemic and related other financial hardships, active study participants will receive a \$100 gift card after the completion of each research MRI study (4 cards total up to \$400).
2. The control group will receive a one time \$50 gift card for their participation in the study

Title: Neurodevelopmental Outcomes in Craniosynostosis Repair
PI: [name]
Site: Arkansas Children's Hospital
Funding: UAMS Intramural Grant

References

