The main objective of this project would be to begin to explore the relationship of CVR and its requisite effects on the growing brain with a cohort of patients who are set to undergo CVR, while performing a battery of neurodevelopmental and imaging studies pre- and post-operatively and compare with normative controls. This is one part of a three-center study collaborating with craniofacial units at Yale University and Wake Forest University in which similar, if not identical protocols will be carried out. We hope that analyses of these data will provide better insight into and greater definition of the effect of CVR and the secondarily available increase in intra-cranial volume on the growing brain in the clinical setting of craniosynostosis.

Relevant Literature and Data

Cranial sutures are dense fibrous connections between adjacent intramembranously-formed bones which permit minor movement to take place. Sutures have several functions:

- a) cranial molding allowing passage through a narrow birth canal by the combined process of sutural overlap and parietal bone deformation,
- b) serving as shock absorbers, (c) permitting brain growth to take place, and
- c) preventing the separation of bones.^{3 4 5} Regardless of the underlying etiology, the early fusion of a suture abolishes further growth of the abutting bones in a direction perpendicular to the suture.

As a consequence, continued enlargement of the brain promotes compensatory overgrowth at other sutures, leading to progressive distortion in the skull shape. Multiple complications can arise because of raised intracranial pressure, facial deformities affecting vision, breathing, and dentition, and other features such as hearing loss, intellectual disability or behavioral issues that might be caused by the underlying gene defect or alternatively might occur secondary to craniosynostosis.^{5 6 7 8 9}

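### Pooled multi-center DTI comparisons have no site or scanner term, and the described pooled record does not list the fields the analysis needs

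*Combined protocol and SAP*

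**What the plan says.** **Pooling.** Aim 2 compares patients with age-matched controls and refers to pooling with other centers. It is unclear whether the controls, the patients or both are pooled. Data Handling, Recordkeeping, and Data Safety Monitoring makes this institution the repository for analysis and describes what comes from outside: "only de-identified, data will be pooled for analysis, ie quantitative data from the DTI analysis and neurodevelopmental results". On identifiers it says "the central database we will keep will ONLY contain the 5-digit IDN", with each institution keeping its own key.

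**Centers.** Background and Rationale, Introduction: "This is one part of a three-center study collaborating with craniofacial units". The same sentence describes the collaboration as one "in which similar, if not identical protocols will be carried out". Dissemination of Data foresees, as a possibility, data "pooled for statistical analysis with the data from our collaborators, Wake Forest, Yale University Departments of Plastic Surgery, and Vanderbilt Department of Plastic Surgery". With this site, that makes four centers.

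**Scanners.** The Radiological Component allows either a 3T Siemens or a 1.5T Philips machine at this site.

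**Controls.** Study Population recruits them from this site's own neurosurgery and plastic surgery clinics. The plan does not say which other centers, if any, supply controls.

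**Analysis.** The endpoints call for comparison with age-matched controls, pre/post comparison, and cohorts by single suture, multiple suture and syndrome. Statistical Methods compares DTI parameters between patients and controls or between ages by unspecified standard methods. It adds that for each MRI session "whether or not the participant was sedated will be a variable including in analysis". No site term, scanner term or harmonization step appears.

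**The concern.** The analysis section and the data-transfer description do not meet. Matching on age, forming the suture and syndrome cohorts, and adjusting for sedation all need fields that the description of the outside-site record does not list.

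The second gap is the model. Scanner differences are already present at this site, and between centers the plan promises protocols that are similar and perhaps identical. If patients come from several centers and controls mainly from one, center and patient status are partly confounded. A constant difference in DTI values between centers then enters the patient-control contrast and would be read as an effect of craniosynostosis. If site and scanner were not recorded with the pooled values, the two could not be separated afterwards.

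**Working it through.** The plan gives no power calculation, significance level, SD or expected center difference, so there is no figure of its own to reproduce. The size below is an illustration.

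**Inputs from the plan.** Up to 500 patients and up to 60 controls (Study Population). These are caps. They are not split by center, and the plan does not say whether they count one site or all. (The 19 listed age groups × 3 give 57 controls, which changes little.)

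**Assumptions.**
- All controls come from this site.
- A share s of patients comes from outside, with a common additive offset d in within-site SD units.
- There is no true patient-control difference, and the test is two-sided at 5%.

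**Patient-control contrast without a site term**

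- Bias = s × d. More generally, it is d times the outside share of patients minus the outside share of controls, so it is zero when every center has the same patient-to-control ratio.
- SE = √[(1 + s(1−s)d²)/n_patients + 1/n_controls].
- False-positive rate = Φ(bias/SE − 1.96) + Φ(−bias/SE − 1.96).

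For s = 0.50, d = 0.3: bias = 0.15; SE = √(1.0225/500 + 1/60) = 0.137; ratio 1.10; rate 19.5%.

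For s = 0.50, d = 0.5: bias = 0.25; SE = √(1.0625/500 + 1/60) = 0.137; ratio 1.82; rate 44.6%.

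| Offset d (500 v 60) | s = 0.33 | s = 0.50 | s = 0.67 |
|---|---|---|---|
| 0.2 SD | 7.7% | 11.3% | 16.5% |
| 0.3 SD | 11.2% | 19.5% | 31.2% |
| 0.5 SD | 22.6% | 44.6% | 68.6% |

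With 120 patients against 60 controls, d = 0.3 gives 9.6% to 24.5% and d = 0.5 gives 17.9% to 55.6% over the same shares.

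**With a site term.** In simulation (3,000 runs per setting) the rate returns to between 4.2% and 6.1%. At s = 0.50 only the 250 patients at this site inform the contrast, so in SD units the SE goes from √(1/500 + 1/60) = 0.137 to √(1/250 + 1/60) = 0.144. It is 0.140 at s = 0.33 and 0.151 at s = 0.67.

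**Within-child pre/post contrast.** A constant center offset cancels by subtraction, and the rate stays at 5.0%. It fails to cancel only if a child changes scanner. Suppose a share q = 0.25 of children changes in one direction, with 100 pairs and pre/post correlation 0.5:

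- Bias = q × d; SE = √{[2(1 − 0.5) + q(1−q)d²]/100}.
- d = 0.3: 0.075/0.101 = 0.74, rate 11.5%.
- d = 0.5: 0.125/0.102 = 1.22, rate 23.1%.

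**The case against.** The strongest reply is that the concern reads silence as exclusion. The sentence on pooled data is about de-identification and is not a transfer specification. It is not clearly a closed list, since the adverse-event section also pools events from all sites and that sentence does not mention them. Age, craniosynostosis type and surgical procedures are collected under this protocol, the other centers are to run similar or identical protocols, and sedation is named as a variable for each session. All of this stands. A reader might infer that the pooled data will certainly lack age, sedation, operation and scanner, or that site adjustment is ruled out. The documents support neither. They show that the required fields are not listed as traveling with outside records, and that the model is left open.

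Three further readings are tempting but not supported:

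- **That center differences bias the effect of surgery in general.** The pre/post endpoint is within child, and a constant offset cancels there. What remains exposed is comparison of post-operative patients with controls, comparison of operations across centers, and pre/post change in a child who changes scanner, which the Radiological Component does not prevent.
- **That five-digit numbers will collide between centers.** Data Handling promises each subject a unique number. The plan does not say who guarantees this across institutions, but any collision probability would rest on an allocation method it does not describe.
- **That the differing center lists show bias.** One passage describes the structure of the study and the other says data may be pooled. They need reconciling, no more.

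It is also fair to say that placing every control at this site is the unfavorable case, because Aim 2 may mean that other centers contribute controls. That limits the size of the problem. It does not supply the missing statement of who contributes what.

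**Conclusion.** The point holds for pooled comparisons between children and should be settled before outside data are transferred. As written, the description of the pooled record does not supply what the analysis section requires, and nothing in the stated analysis separates a center or scanner difference from a patient-control difference.

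In the illustration with half of the patients from outside, the false-positive rate is about 20% at an offset of 0.3 SD and about 45% at 0.5 SD. Those figures depend on the assumed offsets, center shares and control allocation, none of which the documents give. They show how sensitive the comparison is and do not forecast this study's error rate. The problem vanishes if patients and controls are spread over the centers in the same ratio. Single-site analyses escape the between-center part, although the two scanners at this site still call for a scanner term.

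**What to change.** **Data Handling, Recordkeeping, and Data Safety Monitoring.** Replace the description of the pooled data by a list of de-identified fields sent with each scan: site code attached to the ID, scanner and field strength, age at scan, group, operation, time from surgery, suture or syndrome class, sex, sedation, DTI values and test scores. The site code also settles uniqueness of IDs.

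**Statistical Methods.** Include site-scanner as a term in every pooled patient-control model. Estimate that contrast from centers that supply both patients and controls, and let centers without controls inform only within-child contrasts.

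**Center description.** State which centers supply controls, and reconcile the center lists in the Introduction and in Dissemination of Data. The control section also allows published data to replace enrolled controls. If that happened throughout, no center would have both groups and a site term could not rescue the contrast, so the statement should cover this case.

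**Cost.** A transfer specification, a few lines of analysis text and a few model parameters. The standard error rises slightly (0.137 to 0.144 SD at 500 v 60 with half of the patients from outside). Patients from centers without controls add nothing to the patient-control mean difference. Reprocessing all centers' diffusion files through one pipeline would help comparability, but it changes the present arrangement of sharing computed values and is optional.
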